## Debrief interview

Following completion of the observational data collection, each participant who was observed to make an IMG-related error will be invited to take part in a short debrief interview with the Chief Investigator, to provide an understanding of the types of error observed and their causes. There will be a particular focus on how errors relate to the information provided in the monograph. The critical incident technique will be used to investigate whether or not the error was related to the IMG monograph. This approach has been used before to understand the causes of medication errors by exploring the intentions, behaviours and actions of participants involved in a specific situation. Participants will be asked to describe the chain of events leading up to the error, the circumstances in which it occurred, the perceived reasons for the error, and how it might have been prevented.

An interview schedule covering these subjects has been prepared by the Chief Investigator, based on previous relevant research and topic guides . This interview schedule may evolve as data collection progresses, to ensure it adequately reflects issues raised during preceding interviews. Each interview will be audio recorded using a password protected digital recorder, and the interviewer will make field notes. To ensure confidentiality and patient safety, participants will only be invited to take part in an interview when a suitable private room is available and the participant does not have an urgent clinical task to carry out. As soon as practical, the recordings will be transferred to the University of Bath's secure research data storage facility and deleted from the digital recorder. Subsequently, the interview recordings will be transcribed by experienced transcribers employed by the University of Bath. The Chief Investigator will remove any information that could potentially be used to identify a research participant from the transcripts before subsequent analysis and reporting.

## Pilot study

Prior to commencing data collection, there will be pilot observations with five participants to ensure that the data collection process works as expected. Data from the pilot will only be included in the final results if no substantial changes are made to the data collection techniques.

#### Video analysis to investigate observer reliability

To investigate the reliability of the observations, a proportion of the *in situ* simulations will be videoed for subsequent analysis by a second trained observer. A recent systematic review found that interrater reliability was only investigated in 5 of 88 articles describing the observation of medication administration errors. In four of these articles, paired observations took place only during the training of observers and piloting of the study procedures. In one study, paired observations occurred during observer training but also during data collection. There were 528 paired observations of drug administrations of a total of 4271 observed doses (12.4%).

Therefore, in the current study, all five pilot observations and 10% of the main data collection observations will be videoed. The first 12 assessments (5%) will be videoed, with the remaining 12 (5%) being evenly distributed throughout the rest of the study. This distribution of videoed observations will ensure that observations are reliable before the majority of the data are collected, but also allow the on-going reliability to be quantified. During the main (non-pilot) study, if a nurse does not consent to be videoed, they will still be included in the study, but the videoed observation will be moved to the next available consenting participant.

Video recordings will be made using a small high definition camera strapped to the participant's forehead. Preliminary work shows that such a camera captures video of where the wearer is looking in sufficient detail to enable accurate observation of the details of intravenous medicine preparation and administration. Use of a camera strapped to the participant's forehead also ensures that they do not appear in the video, thus preserving their anonymity.

## Missing data

As all data will be collected in a single session, techniques to promote participant retention are not necessary and it is likely that complete data will be obtained from all participants. However, should a participant choose to leave the study before completing *in situ* simulation, their data will be discounted. If a participant completes the *in situ* simulation but does not complete the subsequent secondary outcome measures, the observational data collecting will be included in the final data set, along with their mPDPAI and preference data, if complete.

## Severity determination

Once the *in situ* simulation data collection is complete, the potential severity of each observed error will be determined using a validated method which is appropriate for situations where actual patient outcome is unknown, as in this study. This approach has been widely used in medication errors research, including in studies of the preparation and administration of injectable medicines.

A panel of two experienced physicians (minimum of seven years' experience), three senior pharmacists (minimum of seven years' experience) and two senior nurses (ward manager or more senior, or equivalent) will be sent a brief description of each error with the monograph anonymisation process reversed and asked individually to score the potential clinical significance of each error from 0 (no harm) to 10 (death).

An online survey platform (Online Surveys) will be used to collect these data. No personal data relating to the panel members will be collected via the online survey. Each panel member will be offered a £50 gift voucher in acknowledgement of their contribution.

The validity and reliability of this approach to scoring the potential significance of medication errors has been thoroughly investigated in a study in which 30 healthcare professionals (ten physicians, ten pharmacists and ten nurses) scored 50 medication errors. Ten of these errors were scored twice, two weeks apart. Generalisability theory was used to investigate the reliability of this approach, finding that most of the variance between severity scores was attributable to the inherent differences between the errors. Some of the variance was attributable to the differences between individual panel members, but little was attributable to the occasion on which the error was scored or the professional background of the panel member. Further analysis suggested that a panel of four healthcare professionals (from any profession) would result in a generalisability coefficient of 0.83, which increased with the number of panel members. A generalisability coefficient of 0.8 or more is considered to represent an acceptable level of reliability. In this study, the use of a panel of seven health professionals from a variety of backgrounds will therefore ensure a reliable measure of the severity of the errors observed during the *in situ* simulation.

The same study also investigated the validity of this method, by asking the panel of thirty healthcare professionals to score sixteen medication errors with known outcomes ranging from minor to severe. There was a clear relationship between the known outcome and the panel severity scores, thus establishing the validity of this method. Mean severity scores ranged from 1.1 to 2.3 for errors with a known minor outcome, from 3.3 to 6.5 for errors with a known moderate outcome and from 6.7 to 9.6 for errors with a known severe outcome. The validity of this method in this study will be investigated in a similar way, by asking the panel members to score 15 actual injectable medication errors with a known outcome (five errors each with a known minor, moderate and severe outcome). These errors have been obtained from reports in the literature.

## 4.2 Data management

Data will be entered by the Chief Investigator and double-checked on a separate occasion.

Electronic data will be stored on the University of Bath's secure managed data storage facility. This facility is password protected to ensure security and resilience. Multiple copies are stored in more than one physical location and measures are taken to protect against corruption. Backups are taken daily and kept for three months. A 'previous versions' feature of the storage enables recovery of files.

Anonymous electronic data will be collected at participating sites on a password protected University of Bath laptop computer. Immediately after each data collection session, the latest version of the anonymous study database will be backed up to an encrypted memory stick. At the end of each day on which data are collected (or sooner if a network connection is available), these data will be copied to the University of Bath's secure managed data storage facility.

Paper data collection forms will be stored in a locked cabinet in a locked office at the University of Bath. They will be stored in this location at the first possible opportunity after each data collection session.

## 4.3 Data analysis

#### Observer reliability analysis

Each videoed observation will be independently rated by a trained observer using the same structured observation schedule as was used for the "live" observation. The inter-rater reliability between the live and video observer will be quantified by calculation of Cohen's kappa using each point of the observation schedule as a data point (error vs no error). If the marginal distributions indicate the prevalence problem (observations fall under one category of ratings (error or no error) at a much higher rate than the other), the variant of Cohen's kappa proposed by Byrt *et al.* will be used.

Cohen's kappa will be calculated after the pilot observations are completed. The main study will only commence if Cohen's kappa calculated after the pilot observations is  $\geq 0.80^{[67]}$ . If Cohen's kappa is <0.80, the live and video observers will discuss their ratings to achieve consensus and if necessary, revise the observation schedule and definitions before repeating the pilot study. This process will continue until Cohen's kappa is  $\geq 0.80$ . Cohen's kappa will also be calculated after the first 5% of data collection observations and the procedure described above for the pilot study will be repeated.

Even if Cohen's kappa is  $\geq$ 0.80 after the pilot study and the first 5% of data collection observations, the two observers will still discuss ratings to achieve consensus and apply these findings to the rating of subsequent observations.

#### Statistical analysis of observation data

Statistical analysis will be performed using SPSS, STATA, R and Microsoft Excel.

There are plausible reasons for each of the following participant characteristics modulating the effect size of both the primary and secondary outcomes:

- Participants whose first language is not English.
- Participants with <5 years' experience of administering intravenous medicines, because evidence suggests that the number of errors with which a nurse is involved decreases over the first four to six years of their nursing experience. In particular, one study found that the risk of intravenous medicine administration errors decreased with each year of a nurse's experience up to six years.
- Participants who have previously used the national IMG on a regular basis, as they will be familiar with the layout of the "original" monograph.

Therefore, these characteristics will be considered during the analysis.

First, the data derived from the severity scoring panel will be analysed. The mean severity score allocated by the panel for each confirmed error will be calculated. The potential severity of the outcome for each error will be determined from this mean severity score, as follows:

- Mean severity score <3 = minor outcome
- Mean severity score 3-7 = moderate outcome

• Mean severity score >7 = severe outcome

The inter-rater reliability of the severity scoring panel will be investigated by the calculation of Cronbach's alpha. A coefficient  $\geq$ 0.70 will be considered an indicator of acceptable reliability. The validity of the severity scoring panel will be investigated by comparing the mean severity scores of the actual errors with their known outcomes (minor, moderate or severe).

Subsequently, the moderate-severe IMG-related error rate (primary outcome), the minor IMG-related error rate, and the moderate-severe and minor non-IMG-related error rates will be calculated, based on the above analysis of the severity scores. Following the approach of recent meta-analyses, each error rate will be calculated as a percentage as follows:

 $Error rate = \frac{Number of observations containing one or more errors}{Total number of observations} \times 100$ 

Where one observation contains more than one error, it will be allocated the severity category of the most severe of the individual errors.

Each of these four error rates will then be compared between the two groups using a Chi squared test at the 5% significance level (one test for each hospital site and one for the overall data). This will be followed by a mixed effects logistic regression analysis, with hospital site as the random effect and the other characteristics as fixed effects.

Subject to the distribution of the data, the mean and standard deviation of the time taken for each group to complete the *in situ* simulation will be calculated. These will be compared using time to event analysis (depending on the distribution of the data, probably a Cox proportional hazards model), considering the data from each hospital. The overall data will also be analysed in a similar fashion, with the model incorporating hospital site as a random effect and the other characteristics as fixed effects.

Participant responses to the mPDPAI questions will be used to calculated a modified Decision Conflict Score (mDCS), following the methods described for the original PDPAI. Participants responses to these questions will use a five point Likert scale ranging from strongly agree (scoring 1) to strongly disagree (scoring 5). To calculate a participant's mDCS, the Likert scores will be summed for questions 13 to 20 of the data collection tool, after reversing the scores for question 13, 14, 16 and 17. It will therefore be possible for the mDCS to range from 8 to 40, with a higher score reflecting a higher degree of uncertainty whilst preparing and administering bathicillin.

Individual participants' mDCS will be derived. Subject to the distribution of the data, linear regression will be used to analyse the effects of IMG monograph, hospital, first language, nursing experience and previous IMG experience on the mDCS score.

The psychometric properties of the mPDPAI in the study population will be investigated using the methods used in the initial development of the PDPAI. Item homogeneity will be evaluated by calculating Pearson correlation coefficients between each item and a revised mDCS calculated by removing that item from the total score. Outliers will be defined as items with a correlation coefficient less than 0.2. Inter-item reliability will be investigated by the calculation of Cronbach's alpha. A coefficient the range 0.70-0.90 will be considered an indicator of acceptable reliability.

Previously, construct validity was investigated by hypothesising that there would be a negative correlation between the DCS and participants' rating of the quality of the decision and their satisfaction with it. The same hypotheses will be investigated for the mDCS by calculating Spearman's correlation coefficients between participants' mDCS and their responses to the quality and satisfaction validation questions (questions 21 and 22 in data collection tool). For analysis, the rating scale responses to the satisfaction question question (question 22 in data collection tool) will be transformed into an ordinal scale ranging from 1 ("terrible") to 7 ("delighted"). Negative correlation between these variables will support the credibility of the two hypotheses outlined at the start of this paragraph and the validity of the mPDPAI.

Construct validity will be further investigated by testing two new hypotheses. The first new hypothesis is that that nurses who are more uncertain about how to prepare and administer the dose will take longer to complete this task. This will be investigated by calculating the Spearman's rank correlation coefficient between the mDCS scores and the time taken to complete the *in situ* simulation. Positive correlation between these variable will support the credibility of this first new hypothesis and the validity of the mPDPAI.

The second new hypothesis is that nurses who are more uncertain about how to prepare and administer the dose will be more likely to make one or more IMG-related errors (of any severity). This will be investigated by logistic regression between the mDCS score and the presence or absence of IMG-related errors for each participant. An odds ratio with a 95% confidence interval which does not cross 1.0 will support the credibility of this second new hypothesis and the validity of the mPDPAI.

Participant responses to the monograph preference question (question 23 in data collection tool) will be transformed into an ordinal scale ranging from 1 ("I strongly prefer guide X") to 7 ("I strongly prefer guide Y"). Subject to the distribution of the data, they will be summarised as the mean of all participants' responses and its 95% confidence interval to test the null hypothesis of no preference (mean = 4) at the 5% significance level. To investigate the possible influence of the monograph used for the simulation and hospital site on these data, the difference in mean between the two groups (and 95% confidence interval) will be calculated for each hospital and the overall data. These data will be modelled (logistic regression or Poisson regression, depending on the distribution), with the model incorporating hospital site as a random effect and the other characteristics as fixed effects.

As all data will be collected in a single session under the supervision of the Chief Investigator, full protocol adherence and complete data collection are likely to be achieved for all participants. However, should protocol non-adherence lead to a participant using the IMG version they were not allocated, data will be analysed on an as randomised (i.e. intention-to-treat) basis. Should this occur in more than 5% of participants, a per protocol analysis will also be presented for each outcome. Missing data will be ignored during the analysis, as this is likely to be minimal.

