#### 2.5.2 Secondary outcomes

There will be a number of secondary outcomes:

[figure not shown]
- The rate of IMG-related errors of any severity in each group
- The rate of moderate-severe non-IMG-related errors. This outcome will be measured because it is hypothesised that a more easily understood IMG monograph will enable participants to concentrate more on other aspects of the injection preparation and administration process.
- The rate of non-IMG-related errors of any severity in each group
- The mean time taken to prepare and administer the dose for each group. For each participant, the time will be measured from the point at which they start to read the simulated medication order or IMG monograph until the point at which they inform the observer that they would leave the simulated patient's bedside with the infusion running. This outcome will be measured

because it is hypothesised that a more easily understood IMG monograph will be read and interpreted more quickly, thus reducing the time required to prepare and administer the dose.

- The mean modified Decision Conflict Score (mDCS) for each group. This will be calculated from participant's responses to a modified Provider Decision Process Assessment Instrument (mPDPAI) immediately after they have finished preparing and administering the intravenous infusion. The mDCS is a measure of participants' degree of knowledge and uncertainty whilst making decisions during the preparation and administration of the medicine. It will be measured because it is hypothesised that a more easily understood IMG will result in participants having great confidence in the decisions made during the dose preparation and administration process.
- The mean monograph preference score of each group. Immediately after completing the mPDPAI, each participant will be shown the version of the IMG monograph they did not use to prepare the dose of medicine and asked to rate their preferred version using a seven point Likert scale. This will be measured because it is hypothesised that participants will prefer the more easily used IMG.

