#### 2.7 Sample size

There is one published study that reports the rate of moderate to severe errors in the preparation and administration of intravenous medicines to adults on UK hospital wards and which used the same error observation and severity determination techniques as this study. This study observed one or more moderate-severe errors in 30% of 430 intravenous doses. If the definitions to be used for the current study had been applied in this previous research, 27.2% of 430 intravenous doses would have involved one or more moderate-severe IMG-related errors.

Using the same techniques, a larger and more recent, but as yet unpublished study, observed one or more moderate-severe preparation errors in 28% of 1148 adult injectable medicine doses administered on UK hospital wards. This study did not investigate administration errors, but their inclusion would have increased this error rate.

These error rates are supported by other studies, which either took place in other countries or used different severity determination methods, which report similar rates of moderate-severe preparation and administration errors (22-34% of doses).

Therefore, it is reasonable to assume that participants in the "original monograph" group will make at least one moderate-severe IMG-related error in 30% of doses.

Following discussion with the Study Advisory Group, it was agreed that at least one moderate-severe error occurring in 15% of doses would represent a clinically relevant reduction. This is in line with the assumptions underlying other recent research considering the effect of educational interventions on the rate of injectable medicine preparation and administration errors.

Standard calculations indicate that a sample size of 121 participants per group will give an 80% probability of detecting this reduction in the moderate-severe error rate at the 5% significance level, assuming equal group size. This assumes that there is no clustering of the data by hospital site, as NHS hospitals are required to provide similar training for staff preparing and administering intravenous medicines, and to follow similar procedures.

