## 7. APPENDICIES

#### 11.1 Appendix 1 – Required documentation

- CV of Chief Investigator
- Participant information sheet
- Consent form
- Microsoft Excel data collection tool
- Structured observation schedule
- Debrief interview schedule

Amendment No.	Protocol version no.	Date issued	Author(s) of changes	Details of changes made
1	1.1	31/1/2019	[name]	Excel data collection tool for demographics and participant feedback data changed to paper form
2	1.2	5/6/2019	[name]	Secondary outcomes description amended to make it clear that these will consider the rates of errors of all severity, not just minor errors (not a protocol change, but a clarification). Given the high prevalence of errors found in the project so far and difficulty finding suitable private space, debrief interview procedure amended to specify that only participants making IMG-

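### Section 4.3 compares minor error rates between groups, although section 2.5.2 declares any-severity rates as the secondary outcomes; the minor rate can rise when the user-tested guide works and cannot be read on its own.

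*Protocol*

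**What the plan says.** Protocol section 2.5.2 lists among the secondary outcomes "The rate of IMG-related errors of any severity in each group" and "The rate of non-IMG-related errors of any severity in each group". The moderate-severe non-IMG-related rate is a further secondary outcome, and the moderate-severe IMG-related rate is the primary outcome (section 2.5.1).

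Protocol section 4.3, under the statistical analysis of observation data, sets out which rates are derived. Apart from the primary rate, "the minor IMG-related error rate, and the moderate-severe and minor non-IMG-related error rates will be calculated". For an observation with more than one error, "it will be allocated the severity category of the most severe of the individual errors". The test is then fixed: "Each of these four error rates will then be compared between the two groups using a Chi squared test at the 5% significance level", for each site and overall, followed by a mixed effects logistic regression.

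The amendment history in the appendices records, for version 1.2, that the description of the secondary outcomes was clarified so that "these will consider the rates of errors of all severity, not just minor errors".

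**The concern.** Two current sections describe different quantities. An analyst who follows section 4.3 as written tests the minor IMG-related and minor non-IMG-related rates, which section 2.5.2 does not declare, and does not compare the two any-severity rates that it does declare.

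The substitution matters because of the most-severe rule. A dose can be counted as minor only if it has no moderate-severe error. Each moderate-severe dose that the better guide prevents or downgrades joins the group of doses that can be called minor. A guide that does what it was designed to do can then show a higher minor error rate, tested at the 5% level and open to being reported as harm. Leaving two versions of the outcome in the protocol also allows a choice between them once the results are known.

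**Working it through.** **1. The two sections side by side.**

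| Error class | Declared in 2.5.1 and 2.5.2 | Calculated and compared in 4.3 |
|---|---|---|
| IMG-related | moderate-severe (primary) | moderate-severe |
| IMG-related | any severity | minor |
| Non-IMG-related | moderate-severe | moderate-severe |
| Non-IMG-related | any severity | minor |

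Rows two and four disagree. Elsewhere in section 4.3, IMG-related errors of any severity appear only as the outcome of the regression on the mDCS that examines construct validity. That regression does not compare the monographs.

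**2. Inputs from the protocol (section 2.7).** The original-monograph group is assumed to be one that "will make at least one moderate-severe IMG-related error in 30% of doses". The target with the user-tested guide is 15%. The sample is 121 per group, rising to 172 if recruitment allows, at the 5% level with 80% power.

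**3. The protocol's own figure.** For two proportions, two-sided, without continuity correction:

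n = [1.96 √(2p̄(1−p̄)) + 0.8416 √(p₁(1−p₁) + p₂(1−p₂))]² / (p₁−p₂)²

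With p₁ = 0.30, p₂ = 0.15 and p̄ = 0.225: (1.1575 + 0.4889)² / 0.0225 = 120.5, so 121 per group, with power 80.2%. The stated figure reproduces. The same method is used below.

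**4. What the minor rate measures.** Within one error class, the most-severe rule makes the categories exclusive:

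minor rate = any-severity rate − moderate-severe rate

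If moderate-severe falls by 15 points (30% to 15%) and any-severity falls by D points, the minor rate changes by 15 − D points:

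| Fall in any-severity (D) | Change in minor rate |
|---|---|
| 0 | +15 |
| 5 | +10 |
| 10 | +5 |
| 15 | 0 |
| 20 | −5 |

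**5. Size under an assumption.** The protocol gives no minor or any-severity rate. Let q be the probability of a minor error among doses without a moderate-severe error, taken as equal in both arms. Then minor = (1 − ms) × q and any-severity = ms + (1 − ms) × q, where ms is the moderate-severe rate.

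- q = 40%: minor 0.70 × 0.40 = 28% v 0.85 × 0.40 = 34%. Any-severity 58% v 49%.
- q = 80%: minor 0.70 × 0.80 = 56% v 0.85 × 0.80 = 68%. Any-severity 86% v 83%.

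The chance that the test calls the rise significant is Φ{[|p₂−p₁| − 1.96 √(2p̄(1−p̄)/n)] / √([p₁(1−p₁)+p₂(1−p₂)]/n)}:

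- q = 40%, n = 121: (0.06 − 0.1165)/0.0593 = −0.95, so 17%. At n = 172, 22%.
- q = 80%, n = 121: (0.12 − 0.1223)/0.0619 = −0.04, so 48.5%. At n = 172, 63.1%.

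**6. A less favourable assumption.** If the guide only downgrades errors, any-severity is the same in both arms and the minor rate rises by the full 15 points. For assumed any-severity rates from 50% to 100%, the rise is significant in about 65–80% of trials at 121 per group and 80–92% at 172. The any-severity comparison correctly shows no difference.

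**7. When the minor rate does not rise.** With q free to differ between arms, break-even is at 0.70/0.85 = 0.82. If the guide lowers q by more than about 18% in relative terms, the minor rate falls. For q going from 40% to 20%, it goes from 28% to 0.85 × 0.20 = 17%.

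**8. Non-IMG-related errors.** The same identity applies, but the protocol states no rate for this class, so no size can be given.

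**The case against.** The best defence is that little is lost. Section 2.5.2 is clear about the intended outcome, and the amendment history confirms it. The any-severity rate is the sum of two rates that section 4.3 already calculates. Minor rates in exclusive categories are legitimate quantities if read beside the moderate-severe rates, which section 4.3 also reports. All of that stands, and it limits the weight of the point. It does not supply the missing comparison: section 4.3 names the four rates to be tested, and the any-severity rates are not among them. Nor is this a detail left to a later analysis plan, since the protocol itself fixes the tests, and fixes them on different quantities.

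A reader might infer more than the documents support, in three ways.

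- *That the minor rate must rise if the guide works.* It need not. It is unchanged if any-severity errors also fall by 15 points, and drops if they fall further. Nothing in the protocol says that the guide leaves minor errors untouched.
- *That a significant result in the wrong direction is likely.* The 49% and 63% figures belong to q = 80%. At q = 40% the chance is about 17% at 121 per group. The protocol anchors neither value.
- *That a moderate non-IMG-related error could turn a dose with a minor IMG-related error into a primary event, because the most-severe rule is worded per observation.* Sections 2.5.1 and 2.7 define the primary event by moderate-severe IMG-related errors, Table 1 classifies each error by type, and section 4.3 derives severity for each error. The natural reading applies the rule within each rate; the other reading would contradict those sections.

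**Conclusion.** The point holds as a conflict between two current sections of the protocol. Two declared secondary outcomes, the any-severity IMG-related and non-IMG-related rates, have no planned between-group comparison, and two undeclared minor rates are tested in their place. This part needs no assumption.

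The second part is conditional. Under the most-severe rule the minor rate is a difference of two rates, so it can rise when the guide works and is not interpretable alone. For IMG-related errors at the protocol's target, it rises whenever any-severity errors fall by less than 15 points. How often that would reach significance depends on rates the protocol does not give: about 17% to 49% at 121 per group for q between 40% and 80% with q equal in both arms, and more if the guide mainly downgrades errors.

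The primary outcome, its test and the sample size of 121 per group are not affected.

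**What to change.** In section 4.3, replace the minor IMG-related and minor non-IMG-related rates with the IMG-related and non-IMG-related error rates of any severity, each defined as observations with one or more such errors divided by all observations. Apply the chi-squared tests and the mixed effects logistic regression to these. If minor-only rates are wanted, show them descriptively beside the moderate-severe rates.

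As an optional clarification, add a clause saying that the most-severe rule operates separately within IMG-related and within non-IMG-related errors.

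The cost is a few words in one section. No new data, recruitment or scoring is needed. The change should be made before the allocation codes are revealed for analysis, so that the choice between the two definitions cannot depend on the results.
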